8.6.2.7.2. QTcF Prolongation, Torsades de Pointes, and Other Ventricular Arrhythmias

Subjects who experience >480 ms QTcF prolongation must be monitored closely with ECGs, performed twice weekly for the first week of the QTcF prolongation and then weekly thereafter until the QTcF prolongation is resolved. QTcF prolongation \geq Grade 3, either serious or non-serious and whether or not causally related, must be recorded as an AE or SAE in the eCRF within 24 hours of the assessment, with the investigator's assessment of seriousness, causality, and a detailed narrative.

Monitoring in subjects with QTcF prolongation will include the following:

- Electrolytes (potassium, calcium, and magnesium) should be checked and supplementation given to correct any values outside the normal range.
- Concomitant medications should be reviewed to identify and, if appropriate, discontinue any medication with known QT prolonging effects.

8.6.2.8. Overdose

An overdose is defined as the accidental or intentional administration of any dose of a product that is considered both excessive and medically important. All occurrences of overdose must be reported to the Sponsor within 24 hours of awareness and recorded via SAVER/overdose form or eCRF.

An "excessive and medically important" overdose includes any overdose in which either an SAE, a non-serious AE, or no AE occurs and is considered by the investigator as clinically relevant, ie, poses an actual or potential risk to the subject. Occupational exposures must be reported via the SAVER form.

8.6.2.9. Pregnancy

It is the responsibility of the investigator or designee to notify the Sponsor of any pregnancy while receiving or within 6 months of the dose of quizartinib or dabigatran etexilate in a female subject or a male subject's female partner using the Exposure In Utero (EIU) Reporting Form.

Although pregnancy is not technically an AE, all pregnancies must be followed to conclusion to determine their outcome. If a pregnancy is reported, the investigator should inform the Sponsor within 24 hours of learning of the pregnancy as this information is important for drug safety and public health concerns.

The investigator should make every effort to follow the female subject or partner of a male subject (upon obtaining written consent from partner) until completion of the pregnancy and record the complete pregnancy outcome information, including normal delivery or induced abortion. Any adverse pregnancy outcome, either serious or non-serious, should be reported in accordance with study procedures. If the outcome of the pregnancy meets the criteria for immediate classification as an SAE (ie, post-partum complications, spontaneous or induced abortion, stillbirth, neonatal death, or congenital anomaly, including that in an aborted fetus), the investigator should follow the procedures for reporting SAEs. For reports of pregnancy in the female partner of a male subject, the EIU Reporting Form (or SAE form if associated with an adverse outcome) should be completed with the subject's ID number, initials, and date of birth, and details regarding the female partner should be entered in the narrative section.

8.6.2.10. Pregnancy Testing

Women of childbearing potential will have a serum pregnancy test conducted at Screening and a urine pregnancy test at Day -1 and Day 12 (early termination [ET]/EOS).

For women of childbearing potential (as defined in Section 5.2), document the results of the negative serum pregnancy tests at Screening. For eligibility, a serum pregnancy test must be performed with the results available prior to enrollment.

Women who are postmenopausal will have an FSH test conducted at Screening.

8.6.3. Clinical Laboratory Evaluations

Clinical laboratory evaluations will be performed as detailed in the SoEs in Section 1.3.

The clinical laboratory tests will include hematology, coagulation, blood chemistry, and urinalysis. Subjects will have to fast (except water) for at least 10 hours before having blood drawn for these lab tests. Refer to Section 10.2 for the complete list of laboratory parameters.

Abnormal laboratory values occurring during the clinical study will be followed until repeat test results return to normal (or baseline), stabilize, or are no longer clinically relevant. New or worsened clinically relevant laboratory abnormalities should be recorded as AEs.

Urine test for drugs of abuse (illegal and/or prescription), including tobacco and alcohol will be tested during Screening and Day-1. HBsAg/ HCV/HIV will be tested during Screening.

8.6.4. Physical Examinations

Physical examination will be performed as detailed in the SoE in Section 1.3.

A complete physical examination should include a height (at Screening only), weight (at Screening, Day -1, and Day 12 [ET/EOS]), and calculation of BMI (at Screening only), and an evaluation of the head, eyes, ears, nose, and throat and the cardiovascular, dermatological, musculoskeletal, respiratory, gastrointestinal, and neurological systems. Any abnormality identified at baseline should be recorded. At subsequent visits (or as clinically indicated), limited, symptom-directed physical examinations can be performed at the discretion of the investigator. Changes from baseline abnormalities should be collected in the subject's study record. New or worsened clinically relevant abnormalities should be recorded as AEs.

8.6.5. Vital Signs

Vital signs will be performed as detailed in the SoE in Section 1.3.

Allowable time windows for vital sign assessments are provided in Section 10.7.

Vital signs will include the measurements of respiratory rate, heart rate, systolic and diastolic blood pressures, and temperature. Vital signs will be measured after the subject has rested in a supine position for at least 5 minutes, prior to laboratory draws, and at the same timepoints as ECGs.

8.6.6. Electrocardiograms

Electrocardiograms will be performed as detailed in the SoE in Section 1.3.

Allowable time windows for ECGs are provided in Section 10.7.

TriPLICATE 12 LEAD-ECGS (APPROXIMATELY 2 MINUTES APART) WILL BE PERFORMED AT LEAST 5 MINUTES BEFORE ANY BLOOD COLLECTION AND WILL BE RECORDED FOR EVERY SUBJECT. THE ECG WILL BE MEASURED AFTER THE SUBJECT HAS RESTED IN A SUPINE POSITION FOR AT LEAST 5 MINUTES. 12-LEAD ECG SHOULD BE RECORDED IN TRIPPLICATE WITH THE CLINICAL SITE'S EQUIPMENT (3 SEPARATE ECGS AT LEAST 2 MINUTES APART; THE AVERAGE OF THE 3 QTcF DETERMINATIONS USED TO DETERMINE SAFETY PARAMETERS). ECGS SHOULD BE OBTAINED ONCE, IN TRIPPLICATE, AT SCREENING, ON DAY -1, AND ON DAY 12 (ET/EOS). ON DAY 1 OF PERIOD 1, TRIPPLICATE ECGS WILL BE RECORDED WITHIN 1 HOUR PRIOR TO DABIGATRAN ETEXILATE ADMINISTRATION AND 2, AND 6 HOURS AFTER DABIGATRAN ETEXILATE ADMINISTRATION. ON DAY 5 OF PERIOD 2, TRIPPLICATE ECGS SHOULD BE RECORDED WITHIN 1 HOUR PRIOR TO QUIZARTINIB ADMINISTRATION AND 2, 4, AND 8 HOURS AFTER QUIZARTINIB ADMINISTRATION.

Abnormal, clinically relevant findings occurring post-baseline will be reported as AEs. Whether or not the measurement is performed, the date the ECG is to be performed and results will be recorded.

8.7. Pharmacogenomic (Inherited Genetic) Analysis

A single blood sample for pharmacogenomic (PGx) analysis will be collected predose from each randomized subject. Detailed instructions for the collection, handling, and shipping of samples are outlined in the Laboratory Specifications Document as detailed in Section 10.6.

Genetic analyses will not be performed on blood samples collected for PK or safety assessments. Subject confidentiality will be maintained.

DNA samples will be stored, as outlined in Section 8.7.2 for performing possible PGx analysis in the future; otherwise all remaining DNA samples will be destroyed.

8.7.1. Banking of Specimens for Inherited Genetic Analysis

Procedures for the long-term preservation (banking) of blood and/or DNA specimens extracted from subjects' blood samples for each subject that consented are described in Section 10.6.

The banked samples may be analyzed for genes involved in absorption, distribution, metabolism, elimination, safety, and efficacy of quizartinib. Additionally, samples may be analyzed for genes involved in quizartinib related signaling pathways, or to examine diseases or physiologic processes related to quizartinib. DNA samples will not be immortalized or sold to anyone. This information may be useful in increasing the knowledge of differences among individuals in the way they respond to the study drug, as well as helping in the development of new drugs or improvement of existing drugs.

8.7.2. Storage and Disposal of Specimens

Banked DNA samples will be stored for a maximum of 15 years after the finalization of the clinical study report for this protocol. These specimens will be kept for pharmacogenetic analysis in case new genomic or genetic information is obtained in the future regarding the response (PK) to quizartinib, or in case serious adverse drug reactions are noted in a clinical study and pharmacogenetic analysis is to be conducted for investigation into the cause.

During the storage period, the samples will be coded with labels having no personal information and will not be immortalized or sold to anyone. Subjects will have the right to withdraw consent and have their sample destroyed at any time. However, the data will not be discarded if analysis has been completed before the subject withdraws consent.

8.7.3. Disclosure of the Results of Future Pharmacogenetic Analysis

Because the nature and value of future pharmacogenetic analysis cannot be known at this time, any results obtained from research involving pharmacogenetic samples will not be disclosed to the subject or investigators now or in the future.

9. STATISTICAL CONSIDERATIONS

9.1. Statistical Hypothesis

This is not a hypothesis testing study.

9.2. Sample Size Determination

The number of subjects was not based on statistical power considerations; however, a target sample size of 20 was calculated to provide 90% confidence that the estimated ratios (with and without quizartinib) of dabigatran etexilate geometric mean Cmax and AUC values would be within 10% of true population values. The calculation assumed that AUC and Cmax were log-normally distributed with a within subject coefficient of variation (CV%) of <30% for AUC and Cmax.

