Subjects meeting any exclusion criteria for this study will be excluded from this study. Below is a list limited to the key exclusion criteria:

- Any condition that may affect drug absorption, distribution, metabolism, and excretion.
- History of clinically significant drug allergy.
- Known hypersensitivity to quizartinib, dabigatran etexilate, or their excipients.
- Treatment with any investigational product in a clinical study within 30 days (or 5 drug half-lives, if 5 drug half-lives are expected to exceed 30 days) of Day -1.
- Major surgery within 90 days of Day -1.
- Use of prescription medications including hormonal contraceptives, over-the-counter (OTC) medications, medical marijuana, herbal products, or dietary supplements, other than vitamins and minerals generally consistent with daily requirements, within 14 days of Day -1 (or 5 drug half-lives, if 5 drug half-lives are expected to exceed 14 days).

- History, or presence in the average of triplicate ECGs at Screening and Day -1, of any of the following cardiac conduction abnormalities:
 - QTcF >450 ms
 - Evidence of second- or third-degree atrioventricular block
 - Evidence of complete left or right bundle branch block
 - QRS or T wave morphology that could, in the investigator's opinion, render QT interval assessment unreliable (confirmed with triplicate ECG)
- Use of drugs with a risk of QT interval prolongation or Torsades de Pointes within 14 days of Day -1 (or 5 drug half-lives, if 5 drug half-lives are expected to exceed 14 days).

Investigational Medicinal Product, Dose and Mode of Administration

Quizartinib oral tablet, 30 mg

Dose = 60 mg (2 x 30 mg) single dose on Day 5

Dabigatran etexilate oral capsule, 150 mg

Dose = 150 mg single dose on Day 1 and Day 5

Active Ingredient(s)/INN

[figure not shown]
Quizartinib hydrochloride

Planned Sample Size

The number of subjects was not based on statistical power considerations; however, a target sample size of 20 was calculated to provide 90% confidence that the estimated ratios (with and without quizartinib) of dabigatran geometric mean Cmax and AUC values would be within 10% of true population values. The calculation assumed that AUC and Cmax were log-normally distributed with a within subject coefficient of variation (CV%) of <30% for AUC and Cmax.

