4. STUDY DESIGN

4.1. Overall Design

This is a Phase 1, open-label, 2-period, fixed-sequence, DDI study in healthy male and female subjects designed to evaluate the effect of a single oral dose of 60 mg quizartinib on the PK of a single oral dose of 150 mg dabigatran etexilate. The subject population is described in Section 5. A flow diagram of study activities is presented in [Figure 1.1](#).

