4.1.1. Design Overview

A maximum of 20 eligible healthy subjects will be enrolled. There will be 2 treatment periods: all subjects will receive dabigatran etexilate in Period 1 (Reference Treatment) and quizartinib 2 hours prior to dabigatran etexilate administration in Period 2 (Test Treatment).

Following a Screening Period of up to 21 days where subject eligibility will be confirmed, subjects will be admitted to the clinical research unit (CRU) on the day prior to dosing (Day -1) and remained domiciled in the CRU for the duration of the study. At CRU admission, eligibility will be reconfirmed and baseline safety evaluations, including ECGs recorded in triplicate will be assessed.

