5.4. Screening Failures, Rescreening, and Subject Replacement

Subjects who withdraw or are withdrawn from the study will not be replaced unless approved by the Sponsor.

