9.5.2.2. Statistical Analysis of Pharmacokinetic Endpoints

The PK parameters for dabigatran and for quizartinib and AC886 will be determined using non-compartmental modeling and summarized with descriptive statistics.

To assess the effect of quizartinib on the PK of dabigatran, geometric least square mean (Geo LSM) ratios of Cmax, AUClast, and AUCinf from treatments with and without quizartinib, and their 90% confidence intervals (CIs) will be determined. Each comparison will also be made by performing an analysis of covariance (ANCOVA) on the logarithm-transformed Cmax, AUClast, and AUCinf.

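### Twenty subjects at a within-subject CV of 30% give a 90% interval of about −15%/+17%, not the stated 10%

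*Combined protocol and SAP*

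**What the plan says.** Section 9.2 disclaims a power calculation and rests the sample size on precision: "a target sample size of 20 was calculated to provide 90% confidence that the estimated ratios (with and without quizartinib") of "geometric mean Cmax and AUC values would be within 10% of true population values". The variability assumption follows, that the parameters are "log-normally distributed with a within subject coefficient of variation (CV%) of <30% for AUC and Cmax". The Planned Sample Size entry of the synopsis repeats the claim and the assumption. Neither place gives a formula, a single planning CV or a source for the CV.

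Three other parts of the protocol fix the remaining inputs:

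- **Design.** Section 4.1 describes an "open-label, 2-period, fixed-sequence, DDI study", and every subject receives both treatments.
- **Interval.** Section 9.5.2.2 plans geometric least-squares mean ratios of Cmax, AUClast and AUCinf, and "their 90% confidence intervals (CIs) will be determined".
- **Numbers.** Section 4.1.1 states that "A maximum of 20 eligible healthy subjects will be enrolled", and Section 5.4 that "Subjects who withdraw or are withdrawn from the study will not be replaced unless approved by the Sponsor". The target is therefore also the ceiling, with no routine allowance for dropout.

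**The concern.** All the inputs to the precision statement are given, so it can be checked, and it looks too favourable for a paired comparison at a 30% CV. Section 9.1 says that no hypothesis is tested, so this sentence is the only justification for the sample size and the only statement of expected precision for the primary endpoint. Someone relying on it would expect 90% limits of roughly 0.91 to 1.10 around an estimated ratio. If the real limits are much wider, a small or absent interaction would be reported with considerably more uncertainty than the plan promised.

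**Working it through.** **Inputs.** n = 20, 90% confidence, a 10% limit and a within-subject CV with upper bound 30% (Section 9.2); a two-period paired design (Section 4.1); a two-sided 90% CI (Section 9.5.2.2). I assume 20 complete pairs and a within-subject analysis with n − 1 = 19 degrees of freedom.

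**Precision at the stated bound.**

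- Log-scale within-subject SD: σ_w = √ln(1 + CV²) = √ln(1.09) = 0.2936.
- A within-subject log difference has variance 2σ_w², so SE = σ_w·√(2/n) = 0.2936 × √(2/20) = 0.0928.
- 90% half-width: t(0.95, 19) × SE = 1.729 × 0.0928 = 0.1605.
- Limits: exp(±0.1605) = 0.852 and 1.174, or −14.8%/+17.4%. With the normal quantile they are −14.2%/+16.5%.

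**Confidence of being within 10%.** With the limit at ln 1.1 on both sides, 2Φ(0.0953/0.0928) − 1 = 0.695. For an estimate between 0.90 and 1.10 times the truth, the probability is 0.720.

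**Trying to reproduce n = 20 at a CV of 30%.** I varied the quantile (t or normal), the 10% limit (ln 1.1, −ln 0.9 or 0.10) and the SD (log SD or raw 0.30). With the paired variance, two-sided readings need 43 to 56 subjects and one-sided readings 26 to 34. With the log SD and t, the two-sided figures are 54 (limit ln 1.1) and 44 (limit −ln 0.9). For 90% probability of falling between 0.90 and 1.10, 47 are needed. None gives 20.

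Dropping the factor 2, which treats the within-subject CV as the SD of the paired difference, gives 0.893 to 1.120 (t) or 0.898 to 1.114 (normal) at n = 20. That is near 10% on the lower side only.

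**Lower CVs, n = 20.**

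| CV | σ_w | SE | 90% limits (t) | P(0.90 to 1.10) |
|---|---|---|---|---|
| 30% | 0.2936 | 0.0928 | 0.852–1.174 | 0.72 |
| 25% | 0.2462 | 0.0779 | 0.874–1.144 | 0.80 |
| 20% | 0.1980 | 0.0626 | 0.897–1.114 | 0.89 |
| 18% | 0.1786 | 0.0565 | 0.907–1.103 | 0.92 |

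Setting the half-width equal to the limit and solving for CV gives the largest CV that meets the claim:

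- 17.6% (t, ln 1.1)
- 18.5% (normal, ln 1.1)
- 19.4% (t, −ln 0.9)
- 20.5% (normal, −ln 0.9)

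**Fewer completers, CV 30%.** These counts are illustrations, since the protocol gives no dropout rate. Eighteen completers give 0.843 to 1.186, and sixteen give 0.834 to 1.200.

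**The case against.** The strongest reply is that the CV is given as a bound, not a planning value. If the true CV were 15 to 18%, the design would roughly meet its target, and no document shows that it is higher. This is a fair limit on the finding: −15%/+17% is the result at 30%, not a forecast of what the trial will observe. It does not rescue the sentence, which offers the bound as sufficient for the claim. The claim fails from somewhere between 17.6% and 20.5% up to 30%.

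A second reply is that the sponsor may have meant the variability of the within-subject ratio. Without the factor 2, the lower limit meets 10% exactly at a CV of 29.2% (normal) or 27.8% (t), which fits the stated bound. That is a plausible origin for the 20, but it is inference because no formula is shown. The text calls the quantity a within-subject CV, and even on this reading the probability of falling between 0.90 and 1.10 is 0.873 at 30%.

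Third, no test, margin or decision rule depends on the 10%, and interpretation will rest on the observed intervals. That is true, and it confines the damage to the planning statement. It does not make a wrong figure acceptable as the sole basis for the sample size.

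**Conclusion.** The concern holds. At the CV bound the protocol states, 20 completers give a 90% CI factor of 0.85 to 1.17 and about 70 to 72% confidence of being within 10%, against the 90% claimed. At that CV the claim would need 44 to 54 completers. With 20, it needs a CV of about 17.6% or less to satisfy every reading considered, or 20.5% on the most lenient.

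This rests on log-normality, complete pairs, a within-subject analysis and the usual meaning of within-subject CV. The primary estimates and their confidence intervals are not affected; the stated operating characteristic is. It should be corrected because it is given twice and nothing else supports the sample size.

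**What to change.** Keep 20 subjects and replace the precision statement in Section 9.2 and the synopsis with text such as: *With 20 completing subjects and a within-subject CV of 30%, the 90% CI for the geometric mean ratio is expected to extend from 0.85 to 1.17 times the point estimate (0.84 to 1.19 with 18 completers).*

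If the 10% figure is to stay, state the CV it requires (about 17.5% or less, which satisfies every reading above), give the source for that value, and show the formula.

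In the same edit, change the analyte in Section 9.2 from dabigatran etexilate to dabigatran, to match the synopsis and the primary endpoint in Section 3.1.

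The cost is wording only. The stated precision becomes less favourable, and no subjects or procedures are added.

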9.3. Exposure and Compliance

As the dose administration is under the control of the study sites, compliance to study medication will not be an issue. Study drug administration will be summarized by subject, treatment, and time of dosing.

9.4. Population for Analysis Sets

9.4.1. Pharmacokinetic Population

The PK analysis will be performed using the PK Population defined as all evaluable subjects who received at least 1 dose of study drug (quizartinib or dabigatran) and has a measurable concentration.

9.4.2. Safety Population

The safety analysis will be performed using the Safety Population defined as all subjects who receive at least 1 dose of dabigatran etexilate or quizartinib.

9.5. Statistical Analysis

The statistical analysis plan (SAP) will be developed and finalized before database lock and will describe the subject populations to be included in the analyses, and procedures for accounting for missing, unused, and spurious data. This section is a summary of the planned statistical analyses of the primary and secondary endpoints.

9.5.1. Safety Analysis

9.5.1.1. Adverse Events

Treatment-emergent adverse events are defined as new AEs that occur after the first dose of study drug or as AEs that were present prior to first dose of study drug but which worsened in severity after the start of study drug. AEs collected 30 days after the last dose of study drug will not be considered TEAEs unless they are treatment-related. AEs will be coded using the Medical Dictionary for Regulatory Activities (MedDRA). An AE will be assigned to the study

day in which it started, even if it resolved on a subsequent day. The incidence of TEAEs will be summarized by treatment group. The number and percentage of subjects reporting TEAEs will be calculated overall, by system organ class, by preferred term, and by treatment group.

Treatment-emergent adverse events will be further summarized by common terminology criteria for adverse events (CTCAE) grade and relationship to study drug. Similarly, the number and percentage of subjects reporting treatment-emergent SAEs and related treatment-emergent SAEs will be tabulated, treatment-emergent AESIs, and TEAEs leading to discontinuation of study drug.

A by-subject AE (including treatment-emergent) data listing including but not limited to verbatim term, preferred term, system organ class, CTCAE grade, and relationship to study drug will be provided. Deaths, SAEs, AESIs, and AEs associated with study drug discontinuation will be listed.

